6.3.4 Relationship to Study Drug

The investigator will use the following definitions to assess the relationship of the adverse event to the use of study drug:

- 1) **Definitely Related** An adverse event has a clear temporal relationship to study drug and/or recurs on re-challenge and an Other cause of event is extremely unlikely.
- 2) **Probably Related** An adverse event has a strong temporal relationship to study drug or recurs on re-challenge and an Other cause of event is unlikely or significantly less likely.
- 3) **Possibly Related** An adverse event has a strong temporal relationship to the study drug and an Other cause of event is equally or less likely compared to the potential relationship to study drug.
- 4) **Probably Not Related** An adverse event has little or no temporal relationship to the study drug and/or a more likely Other cause of event exists.
- 5) **Not Related** An adverse event is due to an underlying or concurrent illness or effect of another drug and is not related to the study drug (e.g., has no temporal relationship to study drug or has a much more likely Other cause of event).

If an investigator's opinion of possibly, probably not, or not related to study drug is given, an Other cause of event must be provided by the investigator for the serious adverse event.

6.4 Adverse Event Collection Period

All adverse events reported from the time of study drug administration until 30 days following discontinuation of study drug administration have elapsed will be collected, whether elicited or spontaneously reported by the subject. In addition, serious adverse events will be collected from the time the subject signed the study-specific informed consent.

6.5 Adverse Event Reporting

In the event of a serious adverse event, whether related to study drug, study procedure such as a biopsy, or even if not directly related to any study intervention, the investigator will notify the IRB within 72 hours of being made aware of the serious adverse event. Furthermore, all serious adverse events, in addition to being reported to the FDA by the investigator, must be reported by facsimile within 24 hours to Novartis DS&E at [contact]. Forms can be obtained from, and returned to e-mail: [contact].

The SAE report should comprise a full written summary, detailing relevant aspects of the adverse events in question. Where applicable, information from relevant hospital case records and autopsy reports should be included. Follow-up information should be forwarded to Novartis within 24 hours.

SAEs brought to the attention of the investigator at any time after cessation of LEE011 or everolimus and considered by the investigator to be related or possibly related to LEE011 or everolimus must be reported to Novartis if and when they occur. Additionally, in order to fulfill international reporting obligations, SAEs that are related to study participation (e.g., procedures, invasive tests, change from existing therapy) or are related to a concurrent medication will be collected and recorded from the time the subject consents to participate in the study until he/she is discharged.

For patients enrolled outside of Georgetown University, serious adverse events will also be reported, and all supporting documentation sent (faxed or emailed) to the multi-institutional coordinator and to the Study Chair, [name], as well as to Novartis (as above) within 24 hours. Faxed records should be sent to [contact], with an email to the multi-institutional coordinator and [name] to confirm receipt of those records.

6.6 Pregnancy

In the event of a positive pregnancy test result, study drugs will be immediately discontinued. The investigator must report the positive pregnancy test within 72 hours of the study personnel becoming aware of the pregnancy to the IRB and to Novartis. Patients should also notify the investigator if it is determined after completion of the study that they become pregnant either during the treatment phase of the study or within five days after the treatment period. Information regarding a pregnancy occurrence in a study subject and the outcome of the pregnancy will be collected, and the status of the mother and child should be reported to the IRB and to Novartis after delivery. Pregnancy in a study subject is not considered an adverse event but does require discontinuation of the subject from the study. However, the medical outcome of an elective or a spontaneous abortion, stillbirth or congenital anomaly is considered a serious adverse event and must be reported to the IRB and to Novartis within 72 hours of study personnel becoming aware of the event. Male subjects should also notify the investigators if the subject's partner should become pregnant during the study, this should also be reported within 72 hours of study personnel awareness.

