12. Partial Thromboplastin Time (PTT) must be $\leq 1.5 \times$ upper normal limit of institution's normal range and INR (International Normalized Ratio) ≤ 1.5 . Subjects on anticoagulant (such as warfarin) will be permitted to enroll as long as the INR is in the acceptable therapeutic range as determined by the investigator.
13. Potassium, total calcium (corrected for serum albumin), magnesium, sodium and phosphorus within normal limits for the institution or corrected to within normal limits with supplements before first dose of study medication
14. Patients must have fully recovered from all effects of surgery. Patients must have had at least two weeks after minor surgery and four weeks after major surgery before starting therapy. Minor procedures requiring "Twilight" sedation such as endoscopies or mediport placement may only require a 24-hour waiting period, but this must be discussed with an investigator.
15. Patients and their partners must avoid pregnancy during the trial, and for 21 days after stopping the study medications
 - Avoidance of pregnancy may include total abstinence when this is in line with the preferred and usual lifestyle of the patient. Periodic abstinence (e.g., calendar, ovulation, symptothermal, post-ovulation methods) and withdrawal are not acceptable methods of contraception
 - Eligible female patients may have undergone surgical bilateral oophorectomy with or without hysterectomy, total hysterectomy, or tubal ligation at least six weeks before taking study treatment. In case of oophorectomy alone, patients are eligible only when the reproductive status of the woman has been confirmed by follow up hormone level assessment
 - Eligible male patients and male partners of patients must also agree to avoid pregnancy during the trial, and for 21 days after stopping the study medications
 - Women of childbearing potential must have a negative serum pregnancy test within 14 days prior to initiation of treatment and/or postmenopausal women must be amenorrheic for at least 12 months to be considered of non-childbearing potential
16. Patient is capable of swallowing pills whole
17. Patient is capable of understanding and complying with parameters as outlined in the protocol and able to sign and date the informed consent, approved by the Institutional Review Board (IRB), prior to the initiation of any screening or study-specific procedures

Table 4. ECOG Performance Status

Grade	ECOG

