4.2.1.11 Pregnancy Test

For female subjects of childbearing potential, a serum pregnancy test will be performed at the Screening Visit within 14 days of C1D1 and a urine pregnancy test will be done at the C1D1 visit prior to the first dose of study drug. Subjects considered not of childbearing potential must be documented as being surgically sterile or post-menopausal (for at least 1 year). The test results must be reviewed and determined to be negative prior to dosing. If the urine pregnancy test is positive at C1D1, it should be confirmed by a serum pregnancy test. The test may be repeated at the discretion of the investigator at any time during the study. Should a female study subject become pregnant or suspect she is pregnant while participating in this study, she should inform the treating Investigator immediately.

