4.4 Detailed Patient Assessments

Subject assessments (physical examinations, vital signs, performance status, chemistry, hematology, medication review, and adverse event evaluations) will be conducted at screening, Cycle 1 Day 1, every 2 weeks thereafter until the first response assessment at 8 weeks, and then every 4 weeks thereafter. Study visits and the on-treatment tumor biopsy may be performed 3 days before or after the scheduled date due to unforeseen or unavoidable circumstances, and attempts should be made to schedule visits to line up with the start of a new cycle (within the constraints of the above parameters). Study drugs will be dispensed at the last visit prior to the start of the next 28 day cycle. The radiologic first response assessment at 8 weeks, and subsequent radiologic response assessments every 8 weeks thereafter, may be performed up to 7 days before or after the scheduled date due to unforeseen or unavoidable circumstances. Details are provided in Table 5, and a checklist highlighting the important events for screening through the completion of the trial is provided below, as Table 6.

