4.4.10 Longitudinal Outcomes Assessment

Subsequent therapies will be administered at the discretion of the treating physician. Patients will be followed after progression until death (or up to 24 months) to assess overall survival. Information pertaining to survival and post-treatment therapy will be collected approximately every 12 weeks (Month 3, 6, 9, 12, 15 and 18) beginning after the final visit, for a period up to 24 months.

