Research serum sample for ctDNA _____
Tumor biopsy (optional) _____

Follow-up assessment(s)

Subject assessment (may be done via phone) _____
Vital status data collection _____

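### Section 6.6 asks for notice of pregnancies arising up to five days after treatment, although avoidance runs 21 days, and its 72-hour manufacturer deadline for serious pregnancy outcomes conflicts with 24 hours in Section 6.5

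*Combined protocol and SAP*

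**What the plan says.** **Avoidance period.** Section 3.2, item 15: "Patients and their partners must avoid pregnancy during the trial, and for 21 days after stopping the study medications". The same item applies the 21 days to male patients and male partners.

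**Notification.** Section 6.6 asks patients to report a pregnancy discovered after study completion if it began "either during the treatment phase of the study or within five days after the treatment period". For partners it says: "Male subjects should also notify the investigators if the subject's partner should become pregnant during the study". Section 4.2.1.11 adds a general request to a woman who is or may be pregnant "while participating in this study, she should inform the treating Investigator immediately".

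**Contacts after treatment.** Section 4.4.10: "Information pertaining to survival and post-treatment therapy will be collected approximately every 12 weeks", starting after the final visit. The follow-up block of Table 8 lists "Subject assessment (may be done via phone)" and vital status.

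**Reporting deadlines.** Section 6.5 says of all serious adverse events that they "must be reported by facsimile within 24 hours to Novartis", repeats 24 hours for patients enrolled at other sites, and gives the IRB 72 hours. Section 6.6 classes abortion (elective or spontaneous), stillbirth and congenital anomaly as serious adverse events and gives 72 hours for both the IRB and the manufacturer.

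**The concern.** The protocol sets a 21-day period after treatment in which conception must be avoided, but its post-study request to notify covers only the first five of those days. A patient who conceives later in the period can read Section 6.6 as not asking her to say so, and no scheduled follow-up item mentions pregnancy. The partner wording leaves the same period uncertain.

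The second mismatch is between two deadlines for the same class of event. Section 6.6 is where a site would naturally look when a pregnancy ends badly, and it gives a longer manufacturer deadline than the general rule. What is at stake is the completeness and speed of safety reporting, not the efficacy result.

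**Working it through.** No sample size, power or error rate is involved. The check sets the stated windows side by side and takes two differences.

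| Item | Window | Source |
|---|---|---|
| Avoidance of pregnancy after the last dose | 21 days | 3.2, item 15 |
| Onset of pregnancy covered by the post-study request | 5 days | 6.6 |
| Serious pregnancy outcome to manufacturer | 72 hours | 6.6 |
| Any serious adverse event to manufacturer | 24 hours | 6.5 |
| Listed serious adverse events to DSMC | 24 hours | 6.3.2 |
| Serious adverse event to IRB | 72 hours | 6.5 and 6.6 |

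**Step 1: the notification gap.** The five days limit when the pregnancy begins, not how soon it must be notified. 21 − 5 = 16 days (days 6 to 21), and 16/21 = 76% of the avoidance period.

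**Step 2: does another provision cover those days?**
- Section 4.2.1.11 would cover all of them, leaving 0 of 21 uncovered, if survival follow-up is participation. The documents do not define this. Section 4.4.9.1 withdraws a subject from the study at progression, Section 4.4.10 starts survival follow-up after the final visit, and Table 7 puts follow-up after its off-study column. This leans towards follow-up not being participation, but does not settle it.
- Section 4.4 defines the content of an assessment: "Subject assessments (physical examinations, vital signs, performance status, chemistry, hematology, medication review, and adverse event evaluations)". Pregnancy is not listed. Table 7 marks only survival under follow-up and schedules pregnancy tests only at screening and Cycle 1 Day 1.
- Section 6.4 collects adverse events for 30 days after treatment, but Section 6.6 states that pregnancy itself is not an adverse event.
- The final visit (Section 4.4.9.2) takes place as soon as possible after discontinuation, so it may come before a conception on days 6 to 21 has happened or could be known.

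**Step 3: partners.** Section 6.6 limits the request to the study period. The 21 days are covered only if follow-up is part of the study.

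**Step 4: the manufacturer deadline.** 72 − 24 = 48 hours at most. Neither section states an exception. Section 6.3.2 also uses 24 hours, to the DSMC, and names congenital anomaly and both kinds of abortion (stillbirth is not named there). The IRB deadlines agree. The 72 hours in Section 6.6 for a positive test alone is not a conflict, because pregnancy is not an adverse event.

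**The case against.** The best case for leaving the text alone has five parts.

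- **Patients read the consent form, not Section 6.6.** The consent pages were not available. If they ask for notice over 21 days or more, the effect on patients does not arise. This stands as a limit on the consequence; it does not remove the mismatch in the protocol.
- **Other duties narrow the gap.** Medical history is reviewed at each visit and at the off-study visit. Adverse events are collected for 30 days. Related or possibly related serious events go to the manufacturer whenever they come to light. The investigator's own duty to report a positive test has no five-day limit. All true, and the gap is therefore confined to the patient's self-notification. These duties do not close it: pregnancy is not an adverse event, the final visit can come too early, and the investigator's duty begins only once staff know.
- **76% is a share of calendar days, not of risk.** Correct. Patients have refractory metastatic disease, women of childbearing potential must test negative at entry, and all must avoid pregnancy, so events should be very rare.
- **Section 6.6 may be the specific rule and 6.5 the general one.** Possible, but 6.5 covers all serious adverse events and neither section says the other gives way. A site that meets 24 hours satisfies both, so the conflict matters only where a site relies on 6.6.
- **Nothing visible shows that five days, rather than 21, is the mistaken figure.** Also correct. But while the protocol requires 21 days of avoidance, a shorter notification window does not serve it.

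**Conclusion.** Both inconsistencies are in the current text and nothing elsewhere reconciles them. Followed as written, Section 6.6 can miss notifications inside the protocol's own avoidance period and can lead a site past the Section 6.5 deadline.

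The size is 16 of 21 days (76%) if survival follow-up is not participation and 0 of 21 if it is, plus a delay of at most 48 hours in reaching the manufacturer. The documents do not say how many patients are of childbearing potential or have such partners, so no event count is given; it is assumed to be very small in a trial of at most 44 evaluable patients. This is a minor safety-reporting correction worth making, with no effect on the design or the efficacy analysis.

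**What to change.** Make three wording changes in Section 6.6:

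1. Replace the five-day limit with at least 21 days after the last dose.
2. State the same window for partner pregnancies, in place of the reference to the study period.
3. Set the manufacturer deadline for pregnancy outcomes classed as serious adverse events to 24 hours, as in Section 6.5, and leave the IRB deadline at 72 hours.

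This adds no visits, tests or data collection. The consent form needs a matching change only if it repeats the five-day window.

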6.7 Toxicity Management and Dose Adjustments

6.7.1 Dose Reduction and Delays

6.7.1.1 Known toxicities of LEE011 and/or everolimus defined as dose-limiting toxicities (DLTs)

For the Phase I portion of the trial, toxicities will be defined as DLTs if they are included below (as defined by CTCAE v.4.03) AND they occur during the first 4 weeks of therapy AND are deemed related to the study regimen as assessed by the investigator:

Table 10. Criteria for Defining DLTs Related to LEE011 or everolimus

Toxicity	DLT (per CTCAE v. 4.03)
Hematology	≥ Grade 4 neutropenia (ANC < 500/ μ L) lasting ≥ 7 consecutive days
	≥ Grade 4 thrombocytopenia
	Grade 3 thrombocytopenia with clinically significant bleeding
	Grade 3 or 4 febrile neutropenia
ECG QT interval	QTc interval ≥ 501 ms on at least 2 separate ECGs
Cardiac	≥ Grade 3 cardiac toxicity, clinical signs of cardiac disease such as unstable angina, myocardial infarction, or troponin ≥ Grade 3
Gastrointestinal	≥ Grade 3 vomiting ≥ 48 hours despite optimal anti-emetic therapy
	≥ Grade 3 diarrhea ≥ 48 hours despite optimal anti-diarrheal therapy
	(Optimal therapy for vomiting and diarrhea should be based on institutional guidelines with consideration of the prohibited medications listed in these protocol guidelines).
Hepatobiliary	≥ Grade 2 total bilirubin > 7 consecutive days
	≥ Grade 3 total bilirubin
	≥ Grade 2 ALT with a ≥ Grade 2 bilirubin elevation of any duration in the absence of liver metastases
	≥ Grade 3 ALT for > 4 consecutive days
	Grade 4 ALT or AST
	Grade 4 serum alkaline phosphatase > 7 consecutive days
Renal	≥ Grade 3 serum creatinine
Stomatitis	≥ Grade 3 – everolimus is associated with stomatitis. Per the Afinitor® package insert, topical treatments are recommended, but alcohol-, hydrogen peroxide-, iodine-, or thyme- containing mouthwashes should be avoided as they may exacerbate the condition. Antifungal agents should not be used unless fungal infection has been diagnosed.
Pneumonitis	Non-infectious pneumonitis – everolimus is associated with pneumonitis. The use of corticosteroids is suggested for Grade 1-2 pneumonitis, recommended for Grade 3 pneumonitis, and Grade 4 pneumonitis should result in the cessation of everolimus.
Non-hematologic, non-hepatic adverse events	≥ Grade 3 except for the following exceptions:
Exceptions to DLT criteria	Grade 3 or 4 Allergic Reaction
	Grade 3 alopecia
	< 5 days of Grade 3 fatigue
	Grade 3 fever or infection without neutropenia < 5 days duration
	Grade 3 laboratory abnormalities that are responsive to oral supplementation or deemed by the investigator to be clinically insignificant

6.7.1.2 Dose reduction and delays due to toxicities related to known toxicities of LEE011 or everolimus

If a subject experiences a DLT, as defined above in Table 10, the subject will complete the planned activities of the cycle as scheduled (*i.e.*, CT scans and lab tests will be performed per standard of care). The following are guidelines for dose delay and discontinuation of the study drugs:

- 1) All treatment drugs should be discontinued/delayed concurrently until the toxicity resolves to Grade 1 or lower or to baseline if Grade 2 at the time of study entry.

- a. Of note, LEE011 is known to be associated with myelosuppression. Thus, for Grade 2 or 3 neutropenia, anemia, or thrombocytopenia which do NOT meet the definition of a DLT as detailed in Table 10, then treatment will continue without modification.
 - i. Patients who experience Grade 2 or 3 neutropenia, anemia, or thrombocytopenia, while continuing treatment without modification for that cycle, will be followed with weekly CBCs to track the recovery (or worsening) of the myelosuppression
 - ii. Dose modifications for Grade 2 or 3 neutropenia, anemia, or thrombocytopenia as detailed in Table 11 below will then be instituted FOR SUBSEQUENT CYCLES of therapy
 1. Thus, for example, a patient who experiences Grade 3 thrombocytopenia without bleeding at Cycle 1, Day 15 will continue treatment without modification. CBCs will be checked weekly
 - a. If the thrombocytopenia worsens to Grade 4, for example Cycle 1, Day 22, then treatment will be held, and dose reductions will be instituted starting Cycle 2
 - b. If the thrombocytopenia does NOT worsen through Cycle 1, then treatment hold and dose modifications will be followed for Cycle 2, as per Table 11 below
 - iii. For clarity, for any hematologic toxicity that meets the definition of a DLT (even in the Phase II portion), treatment will be held, and doses modified as per Table 11, even within a cycle.
- 2) Subjects may delay retreatment for up to 3 weeks to allow the toxicity to resolve. In the Phase II portion of the study, dose adjustments will be followed, as per Table 11. One dose adjustment is allowed, as delineated in Table 11.

Table 11. Dose Modifications for Toxicities Related to LEE011 or everolimus

Hematologic	
Thrombocytopenia	
Grade 1 ($\geq 75 \times 10^9/L$)	No dose adjustment required

Grade 2 (> 1.5 – $3.0 \times \text{ULN}$)	Hold LEE011 and everolimus If resolved to \leq Grade 1 in ≤ 21 days, then re-initiate at same dose If resolved to \leq Grade 1 in > 21 days or toxicity recurs, Re-initiate LEE011 at one dose level lower, everolimus 2.5 mg Repeat liver enzymes and bilirubin tests twice weekly for 2 weeks following re-initiation If recurs at reduced dose level, discontinue all therapy (off study)
Grade 3 (> 3.0 – $10.0 \times \text{ULN}$)	Hold LEE011 and everolimus If resolved to \leq Grade 1 in ≤ 21 days, Re-initiate LEE011 at one dose level lower, everolimus 2.5 mg Repeat liver enzymes and bilirubin tests twice weekly for 2 weeks following re-initiation If resolved to \leq Grade 1 in > 21 days or toxicity recurs, discontinue all therapy (off study)
Grade 4 ($> 10.0 \times \text{ULN}$)	Discontinue all therapy (off study)
AST or ALT elevation without bilirubin elevation $> 2 \times \text{ULN}$	
Same grade as baseline or increase from baseline Grade 0 to Grade 1 confirmed 48-72 hours later	No dose adjustment required with LFTs monitored per protocol if same grade as baseline or bi-weekly in case of increase from baseline grade 0 to 1
Increase from baseline Grade 0 or 1 to Grade 2 (> 3.0 – $5.0 \times \text{ULN}$)	Hold LEE011 and everolimus If resolved to \leq baseline value in ≤ 21 days, then re-initiate at same dose If resolved to \leq baseline value in > 21 days or toxicity recurs, Re-initiate LEE011 at one dose level lower, everolimus 2.5 mg Repeat liver enzymes and bilirubin tests twice weekly for 2 weeks following re-initiation If recurs at reduced dose level or recovery to \leq baseline value in > 28 days, Discontinue all therapy (off study)
Increase from baseline Grade 0 or 1 to Grade 3 (> 5.0 – $20.0 \times \text{ULN}$)	Hold LEE011 and everolimus If resolved to \leq baseline value in ≤ 28 days, Re-initiate LEE011 at one dose level lower, everolimus 2.5 mg Repeat liver enzymes and bilirubin tests twice weekly for 2 weeks following re-initiation If recurs at reduced dose level or recovery to \leq baseline value in > 28 days, Discontinue all therapy (off study)
Increase from baseline Grade 2 to Grade 3 (> 5.0 – $20.0 \times \text{ULN}$)	Hold LEE011 and everolimus If resolved to \leq baseline value in ≤ 28 days, Re-initiate LEE011 at one dose level lower, everolimus 2.5 mg Repeat liver enzymes and bilirubin tests twice weekly for 2 weeks following re-initiation If recurs at reduced dose level or recovery to \leq baseline value in > 28 days, Discontinue all therapy (off study)
Grade 4 ($> 20.0 \times \text{ULN}$)	Discontinue all therapy (off study)
AST or ALT and concurrent bilirubin elevation	
Normal ALT or AST or total bilirubin at baseline: AST or ALT \geq Grade 2 with total bilirubin $> 2 \times \text{ULN}$ without evidence of cholestasis OR Elevated AST or ALT or total bilirubin at baseline: [AST	Discontinue all therapy (off study)

or ALT >2 x baseline AND > 3.0 x ULN] OR [AST or ALT 8.0 x ULN]- whichever is lower-combined with [total bilirubin 2x baseline AND > 2.0 x ULN]	
QT Prolongation	
For All Grades	
 1. Check the quality of the ECG and the QT value, repeat if needed 2. Check serum electrolytes (potassium, calcium, phosphorus, and magnesium), if abnormal: hold LEE011 and everolimus, correct with supplements as soon as possible and repeat electrolytes until within normal range, then re-initiate at same dose 3. Review concomitant medications for propensity to prolong the QT interval and CYP3A4 inhibitors 4. Check compliance with correct dose and administration of LEE011
QTcF 450-480 ms	Perform steps 1-4 as directed in "For All Grades." No dose adjustment required
QTcF 481-500 ms	
Hold LEE011 and everolimus. Perform steps 1-4 as directed in "For All Grades." Repeat ECG one hour after the first QTcF of ≥ 481 ms.
 
 • Repeat ECG as clinically indicated until the QTcF returns to < 481 ms, restart LEE011 with dose reduced by 1 dose level. Refer to Table 1 for dosing schedule. • If QTcF ≥ 481 ms recurs, LEE011 should be reduced again by 1 dose level. • Repeat ECGs 7 and 14 days after dose resumption and as clinically indicated
QTcF ≥ 501 ms on at least 2 separate ECGs	
Hold LEE011 and everolimus. Perform steps 1-4 as directed in "For All Grades." Transmit ECG immediately and confirm prolongation/abnormalities with central assessment (if applicable). Perform a repeat ECG within one hour of the first QTcF of ≥ 501 ms.
 
If QTcF remains ≥ 501 ms, consult with a cardiologist (or qualified specialist) and repeat cardiac monitoring as indicated until the QTcF returns to < 481 ms.
 
 • If QTcF returns to < 481 ms, LEE011 will be reduced by 1 dose level. Refer to Table 1 for dosing schedule. • If QTcF remains ≥ 481 ms after performing steps 1-4 as directed in "For All Grades," discontinue LEE011. 
Repeat ECGs 7 days and 14 days after dose resumption (then as clinically indicated) for any patients who had therapy interrupted due to QTcF ≥ 501 ms
 
If QTcF of ≥ 501 ms recurs, discontinue LEE011.

QT/QTcF ≥ 501 ms or > 60 ms increase from baseline AND Torsades de pointes or polymorphic ventricular tachycardia, or signs/symptoms of serious arrhythmia	
Discontinue all therapy (off study). Perform steps 1-4 as directed in "For All Grades." Obtain local cardiologist consultation (or qualified specialist), repeat cardiac monitoring as indicated until QTcF returns to < 481 ms

Non-infectious Pneumonitis	
Grade 1-2	Consider steroids, hold LEE011 and everolimus until below Grade 1, re-initiate at same dose
Grade 3	
Trial of steroids, hold LEE011 and everolimus until below Grade 1
 
If recurs, discontinue all therapy (off study)

Grade 4	Discontinue all therapy (off study)
All Other Adverse Reactions	
Grade 1	No dose adjustment recommended, initiate appropriate medical therapy and monitor
Grade 2	
Hold LEE011 and everolimus until \leq Grade 1, treat with appropriate medical therapy and monitor, re-initiate at same dose
 
If recurs at Grade 2, hold LEE011 and everolimus until \leq Grade 1, Re-initiate LEE011 at one dose level lower, everolimus 2.5 mg

Grade 3	
Hold LEE011 and everolimus until \leq Grade 1, treat with appropriate medical therapy and monitor, re-initiate LEE011 at one dose level lower, everolimus 2.5 mg
 
If recurs at Grade 3, discontinue all therapy (off study)

Grade 4	Discontinue all therapy (off study), treat with appropriate medical therapy

Confounding factors and/or alternative causes for increase of total bilirubin should be excluded before dose interruption/reduction. They include but are not limited to: evidence of obstruction, such as elevated ALP and GGT typical of gall bladder or bile duct disease, hyperbilirubinemia due to the indirect component only (i.e. direct bilirubin component ≤ 1 x ULN) due to hemolysis or Gilbert Syndrome, pharmacologic treatment, viral hepatitis, alcoholic or autoimmune hepatitis, other hepatotoxic drugs. For patients with Gilbert Syndrome, these dose modifications apply to changes in direct bilirubin only. Bilirubin will be fractionated if elevated.

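### Table 11 orders a second LEE011 reduction when QTcF ≥481 ms recurs, but section 6.7.1.2 allows one adjustment and Table 1 may have no dose to step down to

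*Combined protocol and SAP*

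**What the plan says.** **Limit on adjustments.** Section 6.7.1.2 item 2 places Table 11 in Phase II: "In the Phase II portion of the study, dose adjustments will be followed, as per Table 11". It then adds: "One dose adjustment is allowed, as delineated in Table 11". The synopsis rules out any dose change within a patient in Phase I.

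**QTcF 481-500 ms (Table 11).** Both drugs are held and steps 1-4 are carried out. Once QTcF is below 481 ms the site is to "restart LEE011 with dose reduced by 1 dose level. Refer to Table 1 for dosing schedule". If QTcF ≥481 ms returns, "LEE011 should be reduced again by 1 dose level".

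**QTcF ≥501 ms on at least two ECGs (Table 11).** Both drugs are held and steps 1-4 are carried out. If QTcF falls below 481 ms, "LEE011 will be reduced by 1 dose level. Refer to Table 1 for dosing schedule". If it stays at or above 481 ms, or if ≥501 ms recurs, the row discontinues LEE011. It mentions neither everolimus nor study status at that point.

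**Step 2 of the common QT work-up.** If electrolytes are abnormal, the site holds both drugs and must "correct with supplements as soon as possible and repeat electrolytes until within normal range, then re-initiate at same dose".

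**Available doses (Table 1).** Level 2 is 300 mg, level 1 is 250 mg, level -1 is 200 mg and level -2 is 150 mg. Nothing lies below.

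**The concern.** The adjustment limit and the recurrence rule apply to the same patient and give opposite answers. A Phase II patient reduced once for QTcF 481-500 ms, whose QTcF again reaches 481 ms, must be reduced a second time under Table 11 and may not be under 6.7.1.2. A site that obeys the row deviates from the section, and the reverse.

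The row also assumes that a lower level exists. Depending on the RP2D that Phase I selects, the site may be told to move to a dose that the protocol does not define, with no fallback instruction.

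At stake are a consistent response to QT prolongation across sites and avoidable protocol deviations. The unstated status after LEE011 is stopped has a small secondary consequence: under the synopsis statistical section, a patient taken off study before 8 weeks for a reason other than progression or death is not evaluable, whereas one kept on study could be counted as progression-free.

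**Working it through.** The point rests on text, so the check sets the rules side by side and counts dose steps. The plan gives no figure of its own to reproduce here.

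**Step 1. Does the limit reach the QT row?** Item 2 of 6.7.1.2 states the limit for Phase II adjustments made under Table 11, and the QT rows are part of Table 11. The item's pointer back to Table 11 makes the two texts circular, but it does not turn two reductions into one.

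**Step 2. Is a second reduction normal in Table 11?** No other row explicitly orders one. Bilirubin Grade 2 shows the contrasting pattern after a reduction: "If recurs at reduced dose level, discontinue all therapy (off study"). Grade 4 thrombocytopenia, Grade 4 neutropenia, Grade 3 febrile neutropenia and Grade 3 other reactions likewise allow one reduction and then stop all therapy on recurrence.

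**Step 3. Which reductions have a dose?** Inputs are the Table 1 levels. Size of a reduction = (starting dose - reduced dose) / starting dose.

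| RP2D | First reduction | Second reduction |
|---|---|---|
| 300 mg | 250 mg (50/300 = 16.7%) | 200 mg (100/300 = 33.3%) |
| 250 mg | 200 mg (50/250 = 20.0%) | 150 mg (100/250 = 40.0%) |
| 200 mg | 150 mg (50/200 = 25.0%) | none |
| 150 mg | none | none |

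At an RP2D of 300 or 250 mg the second reduction is possible but breaks the one-adjustment limit. At 200 mg it has no dose. At 150 mg even the first reduction has none.

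**Step 4. Step 2 of the work-up against the rows.** For a patient with QTcF ≥481 ms and abnormal electrolytes at an RP2D of 300 mg, step 2 read alone gives 300 mg and the row gives 250 mg. The triggers differ too: step 2 waits for normal electrolytes, the rows for QTcF below 481 ms. The 450-480 ms row requires no dose change, so a same-dose restart fits there without conflict. No sentence states which text prevails at ≥481 ms.

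**Step 5. Everolimus after LEE011 is stopped.** The ≥501 ms row starts by holding both drugs. Section 6.7.1.2 item 1 reads "All treatment drugs should be discontinued/delayed concurrently until the toxicity resolves to Grade 1 or lower or to baseline" (if that was Grade 2 at entry), which favours treating the drugs together but is worded as a hold until recovery. The next row, for QT prolongation with serious arrhythmia, stops all therapy and takes the patient off study. The withdrawal list in 4.4.9.1 does not name permanent loss of one drug.

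**Step 6. Simon design.** For the stated boundaries (stop at ≤2 of 11, reject at ≤9 of 26), exact binomial calculation gives a one-sided type I error of 0.0857 at 25% and power of 0.9005 at 50%. Both meet the plan's 0.1 and 90%, and neither uses any Table 11 rule.

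**The case against.** **The limit may not cover this row.** The 6.7.1.2 list opens with patients who have a DLT under Table 10 and calls its contents guidelines, and QTcF 481-500 ms is not a Table 10 DLT. This does not remove the conflict: item 1a of the same list deals with toxicity that is not a DLT, and item 2 governs Table 11 adjustments in Phase II generally.

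**The missing level is not peculiar to QT.** This is correct. At an RP2D of 150 mg, every Table 11 row that asks for one level lower lacks a dose. The QT row is distinctive because it also fails at 200 mg.

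**A reader might infer that the plan sends patients with QTcF ≥481 ms back to full dose.** The documents do not support that. The arrhythmia row also orders steps 1-4, after all therapy has been stopped. If step 2 could override a row, a patient with torsades would be restarted at full dose, which cannot be meant. The steps are a shared work-up and the row sets the dose. What remains is an unstated precedence, relevant only when electrolytes are abnormal.

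**A reader might infer that everolimus alone is permitted after LEE011 stops.** No text authorises it, the regimen under study is the combination, everolimus is already held at that point, and 4.4.9.1 allows withdrawal on medical grounds. What remains is a missing statement of status.

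**Conclusion.** The contradiction between 6.7.1.2 item 2 and the QTcF 481-500 ms recurrence rule is real and should be corrected. It holds for Phase II. Its size is structural: the second reduction conflicts with the limit at two of the four possible RP2Ds (300 and 250 mg) and has no dose at the other two, and the first reduction has no dose at one (150 mg). The step 2 and ≥501 ms points are clarifications, not separate faults of the same weight.

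How many patients would be affected cannot be estimated. The readable text gives no rate of QTcF ≥481 ms, and each point needs a further condition: recurrence after a reduction, abnormal electrolytes, or ≥501 ms that persists or recurs. It would also be wrong to infer that the design's error rates are compromised, since no Simon figure changes. Study status after a LEE011 stop bears only on whether an individual patient counts as evaluable at 8 weeks.

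**What to change.** 1. **Recurrence in the 481-500 ms row.** Either name the second QT reduction in 6.7.1.2 item 2 as an exception to the one-adjustment limit, or replace it with discontinuation on recurrence, as other Table 11 rows do. The clinical lead should choose.
2. **No lower level.** Under either option, require LEE011 to be discontinued when Table 1 has no lower level.
3. **Step 2.** Limit the same-dose restart to QTcF 450-480 ms, and say that the row's one-level reduction applies at ≥481 ms.
4. **≥501 ms row.** Where LEE011 is discontinued, state that everolimus stops as well and whether the patient goes off study, so that 8-week evaluability is settled in advance.

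The reference to Table 9 in section 4.4.6 should read Table 11. That is a clerical slip: Table 9 is the dispensing table.

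The cost is wording only, with no added patients, visits or tests. The downside is that a few patients with a correctable electrolyte cause restart 50 mg lower (17% to 25%, by RP2D). If discontinuation is chosen, some who might have tolerated a two-level reduction lose LEE011 on recurrence.
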